## ASSESSMENT SCHEDULE

Demographics, medical history, current and historical MF-CTCL treatments, clinical status by physician, clinical status assessments, the Visual Analogue Scale (VAS) for pruritus, the Skindex-29, and ongoing adverse events (AEs) and serious adverse events (SAEs) related to Valchlor are collected at the enrollment visit, per routine clinic visits. Any data that is not collected at enrollment or present in the historical patient information will be indicated as not assessed, not applicable or not done, as appropriate. In addition, to appropriately construct change from baseline analyses all baseline data must be verified as such. For example, if a % BSA score is provided at enrollment, it may not represent a baseline disease score if a subject was already using mechlorethamine prior to the collection of that score. The same handling should apply to the PRO questionnaires.

Change in TNMB classification, change in medical history, change in medications with Valchlor and other MF-CTCL treatments, HCU, clinical status by physician, clinical status assessments, VAS for pruritus, the Skindex-29, reports of secondary exposure, and all AEs and SAEs related and unrelated during Valchlor use and >30 days after Valchlor discontinued are collected at follow-up visits during the observation period, as recorded during the routine clinic visit. These visits occur at the physician's discretion (i.e., they are not scheduled per protocol); consequently, the number of follow-up visits will vary across patients. Additionally, the data collected during the visits will be dependent upon routine clinic practice, and thus not all data may be available.

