## ANALYSIS POPULATIONS

This study will enroll approximately 300 MF-CTCL patients who are being treated (newly initiated or continuing treatment) with Valchlor from up to 50 participating university-affiliated hospitals, community hospitals, or community clinics in the United States.

Patients considered 'being treated with Valchlor' are composed of two distinct groups:

- 1) Patients who are newly initiating Valchlor treatment (i.e. patients who have initiated Valchlor within 30 days or fewer prior to enrollment) and,
- 2) Patients who are continuing treatment with Valchlor (i.e. patients who have been on Valchlor for more than 30 days prior to enrollment).

Patients in either group must be treated with Valchlor at enrollment to be eligible for the study.

All consecutive MF-CTCL patients who are receiving Valchlor at participating US centers are eligible for enrollment in the study, regardless of other MF-CTCL therapies received before or at the time of enrollment.

The primary efficacy endpoint will be the proportion of subjects who are responders to treatment at the 12-month timepoint using a  $\geq 50\%$  reduction from baseline in BSA as the definition of a responder in the group of patients who used mechlorethamine plus corticosteroids and possibly another treatment. Since PROVe did not require a specific visit schedule, the primary 12-month analysis will include patients with a post-baseline % BSA score that falls within a window of  $365 \pm 90$  days. Please note that in this observational trial, patients continued on study even if they permanently discontinued mechlorethamine gel for any reason and switched to new therapy. Given this, such patients (15-20%) will be excluded from the analysis at 12 months. A sensitivity analysis will be conducted for the primary analysis using the full dataset. We will compare this to the subset of patients who discontinued mechlorethamine gel (Table 21a).

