The by-time analyses for each visit will provide supportive clinical and statistical mechlorethamine response data over the whole treatment period, before and after the 12 month results. Patient visits were variable throughout the study and no defined patient visits were required in PROVe. Given this construct, the By-Visit analyses of % BSA data, Pruritis VAS, Skin-Dex 29, and the MF/SS CTCL QOL instrument will be constructed from the respective change from baseline that occurred closest to each of the following timepoints 1, 3, 6, 9, 12, 15, 18, 21 and 24 months, and will include data that falls within  $\pm 45$  days of each designated timepoint.

Other secondary endpoints include:

- Overall Response Rate 2 (ORR2) Percent of patients with  $\geq 50\%$  reduction from baseline in % Body Surface Area of disease for at least two consecutive visits.
- Overall Response Rate 4 (ORR4) Percent of patients with  $\geq 50\%$  reduction from baseline in % Body Surface Area of disease for at least four consecutive visits.
- Time to Next Treatment (TTNT). TTNT is defined as the median number of days an individual patient stayed on a treatment before starting a new treatment or adding on an additional treatment.
- Rates of on Study Hospitalization
- Pruritis VAS
- SkinDex-29

- MF/SS CTCL – QOL Instrument

For each endpoint, separate analyses will be done for patients contributing data with IA and IB staging, all staged patients, and all patients regardless of staging. As PROVe is an observational study, an Intent-to-Treat (ITT) population analysis is not applicable. There are no cases where an intention to treat was prevented and therefore no potential for a selection bias in the analyses prespecified in this SAP. This results in a total of 51 analysis types as shown in the Figure 1 below.

Figure 1: Analysis Populations for the PROVe Study

	Patients Contributing Data			Totals:
	IA and IB Staging	All Staged	All Patients with and without Staging	
Primary Endpoint	1	1	1	3
9 By-Time Analyses	9	9	9	27
7 Other Secondary Endpoints	7	7	7	21
			Overall Total:	51

These analyses will be applied to following four (4) analysis populations:

1. Valchlor + corticosteroids + possibly another treatment (primary) (V+C+other)
2. Valchlor + phototherapy + possibly another treatment (V+P+other)
3. Valchlor + oral bexarotene + possibly another treatment (V+B+other)
4. Valchlor + any other treatment (V+other)

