### **Secondary Analyses will include:**

- Percent of patients with  $\geq 50\%$  reduction from baseline in % Body Surface Area of disease at each visit preceding and following the 12 month visit
- Overall Response Rate 2 (ORR2) Percent of patients with  $\geq 50\%$  reduction from baseline in % Body Surface Area of disease for at least two consecutive visits.
- Overall Response Rate 4 (ORR4) Percent of patients with  $\geq 50\%$  reduction from baseline in % Body Surface Area of disease for at least four consecutive visits. Further description of the ORR4 endpoint is shown in [Prince et al 2017].
- Time to Next Treatment (TTNT). Further description of the TTNT endpoint is shown in [Hughes and Prince 2014].
- Rates of on-study hospitalization

- Change from baseline in PRO questionnaires:
  - a. Pruritis VAS
  - b. SkinDex-29
  - c. MF/SS CTCL QOL instrument

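### PRO change from baseline is a secondary analysis, but no questionnaire precedes Valchlor and the SAP names no reference score that meets its own baseline caution

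*SAP*

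**What the plan says.** The SAP's list of secondary analyses includes "Change from baseline in PRO questionnaires", naming the three instruments. Under Analysis Populations, the by-visit results for "Pruritis VAS, Skin-Dex 29, and the MF/SS CTCL QOL instrument will be constructed from the respective change from baseline", using the change "that occurred closest to each of the following timepoints 1, 3, 6, 9, 12, 15, 18, 21 and 24 months", within 45 days either side. The same sentence also governs % BSA.

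On exposure at entry, the SAP states: "Patients in either group must be treated with Valchlor at enrollment to be eligible for the study". New patients are "patients who have initiated Valchlor within 30 days or fewer prior to enrollment"; continuing patients have more than 30 days on drug. Protocol 5.2.1 likewise places a new patient's qualifying office visit after Valchlor has been started.

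The SAP's Assessment Schedule asks that baseline data be verified. It says of an enrollment % BSA score that "it may not represent a baseline disease score if a subject was already using mechlorethamine prior to the collection of that score", and continues: "The same handling should apply to the PRO questionnaires". It names no other score to use.

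**The concern.** A change score needs a reference, and the plan's caution falls on the only scheduled candidate. BSA has a way out, because clinical status assessments are among the pre-treatment data gathered from records at enrollment. The questionnaires have no such source.

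Two competent analysts could therefore follow this SAP to different deliverables. One applies the caution strictly and returns near-empty PRO tables. The other uses the enrollment form and returns change during ongoing treatment. A reader of the second set could take it as change since starting Valchlor. Baseline at Month 12 would also mean different things in Table 22 (BSA) and Table 27 (PROs).

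**Working it through.** **1. What depends on the reference.** SAP Figure 1 reproduces: 3×1 + 3×9 + 3×7 = 51. Three of the seven other secondary endpoints are PROs, so 3 instruments × 3 staging sets = 9 of those 21 analyses. By time point, Tables 27a-c hold 3 instruments × 9 time points × 3 staging sets = 81 cells per treatment population.

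**2. Can a form precede Valchlor?** Let L be the days from Valchlor start to enrollment.
- New patients: 0 ≤ L ≤ 30. Continuing patients: L > 30 (SAP, Analysis Populations).
- Forms are collected at visits during observation, which starts at consent (Protocol 5.3.2 and 5.6.1), so no form is dated before enrollment.
- A pre-Valchlor form would have to be dated more than L days before enrollment. None can be.
- The one possible exception is L = 0 with the form completed before first use. The treatment log records dates, so the order within a day cannot be checked from it.

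**3. Is there a retrospective source?** Protocol 5.3 lists the pre-treatment variables as weight, TNMB classification, treatments and clinical status assessments. In Table 1 of both documents, the asterisk for pre-treatment collection is on those rows and not on the questionnaires. The SAP's section on characteristics at enrollment also lists pre-treatment data and enrollment questionnaires as separate items.

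**4. Apply the SAP's caution.**

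| Reading | Result for Tables 27a-b |
|---|---|
| Strict: an on-drug score is not a baseline | Essentially 0 patients, below the 20 needed for analysis and the 10 needed for reporting (by-time subgroups are exempt from the latter); no imputation is planned |
| Permissive: the enrollment form is the baseline | Tables fill, but show on-treatment change |

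The Table 17 shells label a PRO row as baseline, and Statistical Methods summarizes VAS and Skindex-29 at enrollment. Both concern score levels, and neither is tied to Table 27.

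**5. Allowance for recall.** Skindex-29 and CTCL-QoL ask about the past 4 weeks (Protocol Appendices A and D). The share of the recall period before Valchlor is max(0, 28 − L)/28: 100% at L = 0, 50% at L = 14, and 0% from L = 28. Every continuing patient is at 0%. The VAS form could not be read in the text available, so nothing is assumed about its recall.

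**6. MF/SS-CTCL (Table 27c).** Amendment 1 added this instrument (Protocol section 1).
- Enrolled under Amendment 1: an enrollment form is scheduled.
- Enrolled earlier and still ongoing: re-consent is at the first follow-up visit (Protocol Table 1 footnote), so the first form comes at or after that visit. The original follow-up was 12 months, so this can be up to about 12 months after enrollment. At worst that is at or after time points 1, 3, 6, 9 and 12, or 5 of 9. Actual re-consent timing is not given.
- Already completed one year: not offered continuation (Protocol 5.9), so no form at all.

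The SAP's Assessment Schedule text and its Table 1 do not list the instrument, and no rule covers the second or third group.

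**The case against.** The best defence is that the SAP states a caution and no exclusion rule. For VAS and Skindex-29 the enrollment form is the only scheduled candidate, the Table 17 shells already call such a score baseline, and 4-week recall lets a recent starter's form reach back before Valchlor. This makes the permissive reading the likelier one in practice. But the recall allowance is partial for new patients and nil for continuing ones. The permissive reading also uses the very score the SAP questions, under a label that does not say so.

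Some stronger inferences are tempting but not supported:
- **That the windows have no time origin.** The SAP does not restate one beside the windows, but the documents point to enrollment. Protocol 5.9 equates end of study with Month 24, the 24 months run from original consent, SAP Exposure Definitions start observation at enrollment, and SAP Table 1A counts months on study. Nothing suggests counting from Valchlor start.
- **That the PRO windows are uniquely loose.** The primary BSA rule requires "patients with a post-baseline % BSA score that falls within a window of" 365 ± 90 days, while the by-visit rule has no such word. But the by-visit rule covers BSA too.
- **That Month 1 could return the enrollment form as a zero change.** With Month 1 as day 30, the window does reach back to 30 − 45 = day −15. But a reference form has no change from itself, and SAP Table 1 and the Table 17 shells separate enrollment from follow-up. A clarifying phrase is enough.
- **That the results are biased in a known direction.** The documents give no PRO variability, effect size or distribution of L.

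**Conclusion.** The point holds and should be fixed. The SAP's baseline caution conflicts with its PRO endpoint, and the plan does not say how to resolve this. It affects 3 of the 7 other secondary endpoints at all nine time points. Tables 27a-b will be either near-empty or a record of on-treatment change labelled as change from baseline. Table 27c also lacks an enrollment reference for patients enrolled before Amendment 1, and any score at all for those who had already completed one year.

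The limits are clear. The primary endpoint is unaffected, p-values are declared descriptive, and neither the size nor the direction of bias can be derived. The conclusion assumes that forms were collected only as the protocol schedules them. Time on drug at enrollment is known only as at most 30 days or more than 30 days. The 5-of-9 figure is an upper bound.

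**What to change.** Amend the SAP's Analysis Populations (by-visit paragraph), Assessment Schedule and list of secondary analyses, and Tables 27a-c:

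1. Name the enrollment form as the reference for VAS and Skindex-29. For MF/SS-CTCL, use the enrollment form where it exists. Show patients whose first form came later separately, as change from first completed form, and count patients with no reference form. The separate title matters because follow-up continues after Valchlor is stopped (Protocol 5.1), so a late first form need not be an on-drug score.
2. Title the main results 'change from enrollment (on Valchlor)' and state that they are not pre-treatment changes.
3. State that the by-time windows, for BSA as well as PROs, run from enrollment, in line with the protocol's Month 24. State that only forms completed after the reference form count toward a time point.
4. Report time from Valchlor start to the reference form: median, range and number unknown. Start dates are on the treatment log. A wholly missing start date is not replaced, hence the count of unknowns.

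The cost is SAP wording, new titles and a few summary rows, with no new data collection. The sponsor accepts a less favourable endpoint label and smaller numbers in the main part of Table 27c.

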| Healthcare utilization related to MF-CTCL (as assessed by physician) | | |
| Hospital admissions [‡] | | X |
| Emergency room visits | | X |
| Clinical Status (as assessed by physician) | X | X |
| Clinical Status Assessments* | | |
| Composite Assessment of Index Lesion Severity | X | X |
| Modified Severity Weighted Assessment Tool | X | X |
| Physician's Global Assessment | X | X |
| Body Surface Area of disease | X | X |
| Patient-Completed Questionnaires[§] | | |
| Visual Analogue Scale for pruritus | X | X |
| Skindex-29 | X | X |
| Mycosis fungoides / Sézary syndrome-type cutaneous T-cell lymphoma | X | X |
| Safety Measures^{**} | | |
| AEs and SAEs | X ⁺ | X |
| Reports of secondary exposures | | X [^] |

*Included in pre-treatment data collection, which is performed at enrollment. All data must be completed as available.

[†]Includes collection of start and stop dates for each medication, including reasons for starting and stopping medications. Start and stop dates are also collected for Valchlor, including short gaps in treatment, such as drug holidays.

[‡]For each hospital admission, length of stay and primary admission and discharge diagnoses will be collected.

[§]To be completed by patients who can read and understand English and are able to self-complete the questionnaires based on the investigator's assessment. Patients who are unable to self-complete the questionnaires will not be excluded from the study.

^{**}Safety measures, which include AEs and SAEs, will be collected from the informed consent date and prospectively at every visit during the study and up to 30-days post-discontinuation of Valchlor during the study. Ongoing AE and SAE data will be collected through the end of study, regardless of Valchlor use.

New AEs and SAEs that occur more than 30 days after discontinuation of Valchlor will be reported to Actelion US Drug Safety if investigator feels there is a possible causal relationship with Valchlor. Investigators are also expected to assess patients for AEs and SAEs and follow the appropriate reporting procedures per Section 7.

⁺All ongoing AEs and SAEs for patients being treated [see Section 5.2.1 for definition of “being treated”] with Valchlor.

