5.7.5 Adverse events

The frequency and percentage of patients experiencing any on-study AEs, SAEs, or death will be summarized by system organ class and preferred MedDRA terminology. Additional detail for AEs of special interest (e.g., dermatitis) will be summarized separately. SAEs will be displayed in patient listings, both including and excluding events that were not concurrent with Valchlor exposure. The definition of an on-study event is one that occurs on the day of enrollment or later, but before the date of study discontinuation or completion.

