7.1.2 Serious adverse events

An SAE is defined by the International Conference on Harmonisation guidelines as any AE fulfilling at least one of the following criteria:

Fatal.

Life-threatening: refers to an event in which the subject was at risk of death at the time of the event. It does not refer to an event that hypothetically might have caused death had it been more severe.

Requiring inpatient hospitalization, or prolongation of existing hospitalization.

Resulting in persistent or significant disability or incapacity.

Congenital anomaly or birth defect.

Medically significant: refers to important medical events that may not immediately result in death, be life-threatening, or require hospitalization but may be considered to be SAEs when, based upon appropriate medical judgment, they may jeopardize the subject, and may require medical or surgical intervention to prevent one of the outcomes listed in the definitions above.

The following reasons for **hospitalizations** are exempted from being reported:

Hospitalizations for cosmetic elective surgery, or social and/or convenience reasons.

Hospitalization for pre-planned (prior to enrollment) standard monitoring of a pre-existing disease (present at enrollment) or medical condition that did not worsen, e.g., hospitalization for coronary angiography in a patient with stable angina pectoris.

Hospitalizations for elective treatment of a pre-existing disease (present at enrollment) or medical condition that did not worsen, e.g., elective hip replacement for arthritis.

New AEs and SAEs that occur > 30 days after the discontinuation of Valchlor unless there is a reasonable possibility of causal relationship to Valchlor.

However, complications that occur during such hospitalizations are AEs or SAEs (for example, if a complication prolongs hospitalization) and must be reported as described below.

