\*\*Safety measures, which include AEs and SAEs, will be collected from the informed consent date and prospectively at every visit during the study and up to 30-days post-discontinuation of Valchlor during the study. Ongoing AE and SAE data will be collected through the end of study, regardless of Valchlor use. New AEs and SAEs that occur more than 30 days after discontinuation of Valchlor will be reported to Actelion US Drug Safety if investigator feels there is a possible causal relationship with Valchlor.

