**Skindex-29, Functioning**

Baseline Completed [(mean +/- SD) (min, max)]	n= xx.x +/- xx.x (xx,xx)				
Baseline Not Done [(mean +/- SD) (min, max)]					

Follow-Up Completed	n=	n=	n=	n=	n=
---------------------	----	----	----	----	----

Quarter 1 [(mean +/- SD) (min, max)]	xx.x +/- xx.x (xx,xx)				
Quarter 2 [(mean +/- SD) (min, max)]					
Quarter 3 [(mean +/- SD) (min, max)]					
Quarter 4 [(mean +/- SD) (min, max)]					
Follow-Up Not Done [(mean +/- SD) (min, max)]					

- 
- a. Patients can contribute multiple visits to a quarter. These visits could be categorized as response or non-response for the same patient within a quarter.

Run Date: ddMMMyyyy

Date of Data Extraction: ddMMMyyyy

Helsinn Therapeutics (US),  
 Inc., Protocol AC-079A501  
 (PROVe)

Table 18. Adverse Events

Characteristic	V+C+ Other	V+P+ Other	V+OB+ Other	V+ Other
	n=		n=	n=
Overall a	xx (xx.x)		xx (xx.x)	xx (xx.x)
System Organ Class 1				
Preferred Term A				
Preferred Term B	xx.x +/- xx.x		xx.x +/- xx.x	xx.x +/- xx.x
...				
System Organ Class 2				
Preferred Term C	xx (xx.x)		xx (xx.x)	xx (xx.x)
...				
...				

---

Note: Number of subjects and % of subjects are shown

a. Overall refers to any recorded AE, including AEs reported as ongoing at the time of enrollment

Run Date: ddMMMyyyy

Date of Data Extraction: ddMMMyyyy

Helsinn Therapeutics (US), Inc.,  
 Protocol AC-079A501 (PROVe)  
 Table 19. Serious Adverse Events

Characteristic	V+C+ Other	V+P+ Other	V+OB+ Other	V+ Other
	n= xx (xx.x)	n= xx (xx.x)	n= xx (xx.x)	n= xx (xx.x)
Overall a				
System Organ Class 1				
Preferred Term A				
Preferred Term B	xx.x +/- xx.x	xx.x +/- xx.x	xx.x +/- xx.x	xx.x +/- xx.x
...				
System Organ Class 2				
Preferred Term C	xx (xx.x)	xx (xx.x)	xx (xx.x)	xx (xx.x)
...				
...				

Note: Number of subjects and % of subjects are shown

a. Overall refers to any recorded AE, including AEs reported as ongoing at the time of enrollment

Run Date: ddMMMyyyy

Date of Data Extraction: ddMMMyyyy

Table 20. Continuous vs. Non-Continuous Exposure

Characteristic	Overall	Continuous Exposure (n=xx)	Non-Continuous Exposure (n=xx)
Total days of exposure, mean (SD)	xx.x (xx.x)	xx.x (xx.x)	xx.x (xx.x)
Days of longest continuous exposure, mean (SD)	xx.x (xx.x)	xx.x (xx.x)	xx.x (xx.x)

Helsinn Therapeutics (US), Inc.,  
 Protocol AC-079A501 (PROVe)

Table 21. Percent of patients with  $\geq 50\%$  reduction from baseline in % Body Surface Area of disease at 12 months ( $365 \pm 90$  days)

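### The adverse event tables have no Valchlor window, and the documents disagree on which events are collected more than 30 days after Valchlor stops

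*SAP*

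**What the plan says.** **Collection of late events.** The SAP's Assessment Schedule states that "all AEs and SAEs related and unrelated during Valchlor use and >30 days after Valchlor discontinued are collected at follow-up visits". The Table 1 footnote, which appears in both documents, collects AEs and SAEs "prospectively at every visit during the study and up to 30-days post-discontinuation of Valchlor during the study". It then adds two things:

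- Events already under way: "Ongoing AE and SAE data will be collected through the end of study, regardless of Valchlor use".
- New events beyond 30 days: these "will be reported to Actelion US Drug Safety if investigator feels there is a possible causal relationship with Valchlor".

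Protocol 7.1.2, in its list of items exempt from reporting, includes "New AEs and SAEs that occur > 30 days after the discontinuation of Valchlor unless there is a reasonable possibility of causal relationship". Protocol 7.2 requires SAEs to be collected until 30 days after discontinuation. The same section, and section 5.6.1, place all AEs in the eCRF with no time limit; 5.6.1 adds that this applies whether or not they are related.

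**Follow-up.** Protocol 5.1 follows patients for at most 2 years from consent and does not make staying in the study depend on staying on Valchlor.

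**Analysis.** The footnotes to SAP Tables 18 and 19 say "Number of subjects and % of subjects are shown", and that the overall row takes in every AE on record, including those ongoing at enrollment. The SAP's Statistical Methods section adds no window. Protocol 5.7.5 defines an on-study event as one occurring from enrollment until study discontinuation or completion. It asks for SAE patient listings "both including and excluding events that were not concurrent with Valchlor exposure". SAP Listing 1 has no such split.

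**The concern.** A stated objective in both documents is to estimate the incidence of dermatitis in patients using Valchlor, within the wider objective of describing AE incidence. A percentage that runs to the end of study without regard to Valchlor does not isolate use. It includes events that arise after a patient has stopped and, for some, after a switch to another therapy.

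The reader also cannot tell what that off-drug time contains. Under the Assessment Schedule it would hold all new events. Under the Table 1 footnote it would hold continuing events and, at most, new ones judged possibly related. The same percentage means different things in the two cases.

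The SAP handles this problem for efficacy, where it excludes patients who permanently stopped and switched (given as 15-20%) from the 12-month primary analysis. It has no counterpart for safety.

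**Working it through.** **1. The texts side by side, for a new, unrelated AE starting more than 30 days after Valchlor stops**

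| Source | Is it collected? |
|---|---|
| SAP, Assessment Schedule | Yes |
| Table 1 footnote, SAP and protocol | Outside the collection window |
| Protocol 7.1.2 | Exempt from reporting |
| Protocol 7.2, SAE window | Outside the window |
| Protocol 5.6.1 and the eCRF sentence of 7.2 | Yes; no time limit stated |

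The relatedness condition in the footnote governs reporting to Drug Safety. The limit on collection is the separate 30-day phrase.

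**2. What Tables 18 and 19 count.** They give numbers and percentages of patients with any AE on record, with no end date tied to Valchlor, no split by exposure or relationship, and no person-time. Off-drug events therefore enter under any collection rule. Including AEs already ongoing at enrollment also departs from the on-study definition in protocol 5.7.5. The SAP text limits enrollment AEs to those related to Valchlor, while protocol Table 1 takes all ongoing ones.

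**3. Size.** The documents give no AE rate, so there is no figure to reproduce. What follows is an illustration.

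From the documents:
- d = 15% or 20% permanently stopped and switched (SAP, Analysis Populations), taken as the proportion by month 12.
- Follow-up F = 24 months, or 12 for patients who completed under the protocol before Amendment 1.

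Assumed:
- constant discontinuation hazard λ = −ln(1−d)/12 per month, with no restarts;
- complete follow-up to F;
- the same AE hazard on and off drug, h = −ln(1−c)/24, with 24-month risk c of 10%, 30% or 50%;
- a share r of 0, 25% or 50% of late events recorded because they were judged related.

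The 30 days are taken as 1 month.

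Share of observation time more than 30 days off drug:

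[(F−1) − (1−e^(−λ(F−1)))/λ] / F

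- F = 24: 13.5% (d = 15%) and 17.9% (d = 20%).
- F = 12: 6.5% and 8.8%.

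Difference in the percentage of patients with the AE, full collection minus the 30-day rule:

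Δ = e^(−hrF) · λe^(−h(1−r))/(λ+h(1−r)) · [1 − e^(−(λ+h(1−r))(F−1))] − e^(−hF) · [1 − e^(−λ(F−1))]

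- Largest case: d = 20%, c = 50%, r = 0, F = 24. λ = 0.01860, h = 0.02888, Δ = 0.2528 − 0.1740 = 7.9 points.
- Smallest 24-month case: d = 15%, c = 10%, r = 50%. λ = 0.01354, h = 0.00439, Δ = 0.2474 − 0.2409 = 0.7 points.

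| 24-month risk c | Δ, 24-month follow-up | Δ, 12-month follow-up |
|---|---|---|
| 10% | 0.7-1.8 | 0.2-0.4 |
| 30% | 1.8-5.0 | 0.5-1.4 |
| 50% | 2.6-7.9 | 0.8-2.4 |

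**4. A single-patient scenario as a cross-check.** Assume 0.5 unrelated AEs per patient-year and Valchlor stopped at month 6, so that 7 months fall under full collection.

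- Recorded to 30 days only: 1 − e^(−0.5×7/12) = 25.3%.
- All recorded to month 24: 1 − e^(−0.5×2) = 63.2%. The gap of 37.9 points, times 0.15-0.20, is 5.7-7.6 cohort points.
- All recorded to month 12: 1 − e^(−0.5) = 39.3%. The gap of 14.0 points, times 0.15-0.20, is 2.1-2.8 cohort points.

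**The case against.** **The SAP did not instruct the sites.** They collect under the protocol. SAP version 3.0 is dated November 2019, last patient last visit was planned for Q3 2019, and Table 28 is already filled in with N=289. A reader might infer that some sites followed the SAP sentence and others the footnote, so that the percentages mix two rules. The documents do not support that. If every site entered all AEs at every visit, the tables rest on one rule plus off-drug time. What stands is that the protocol itself points both ways, and nothing says which practice the eCRF reflects.

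**The wording may be a slip.** Read literally, the SAP sentence leaves days 1 to 30 after stopping unnamed, so it may have been meant as up to 30 days. That would align it with the footnote, but not with the untimed eCRF sentences, and it would give Tables 18 and 19 no window.

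**The footnote does not say that only possibly related late events are collected.** That stronger reading is tempting but wrong: continuing events are followed whatever their cause, and the causality condition concerns Drug Safety. Nor does the visit list in the protocol synopsis settle the matter. Its AE item ends with a restriction to time on Valchlor, which may apply only to secondary exposures.

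**Off-drug time is part of the protocol's definition.** This is correct. Section 5.7.5 runs on-study events to the end of study, and its split by concurrence covers SAE listings, not AE tables. A restricted table should therefore be added, not substituted.

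**Listing 9 already carries onset date and relationship.** This is also correct, and with the Valchlor start and stop dates a split could be derived. None is planned.

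**Conclusion.** The point holds in a limited form. The documents conflict on new, unrelated AEs arising more than 30 days after Valchlor stops. Tables 18 and 19 have no Valchlor window although patients remain on study off drug. The SAE listing split in protocol 5.7.5 is missing from the SAP.

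A reader might take 6 to 8 points as the expected distortion. That is the top of an assumed range: it needs a common event, full 24-month follow-up for those who stop, and few or no late events recorded as related. Across the assumptions shown, the choice of rule moves an AE percentage by 0.7 to 7.9 points over 24 months and 0.2 to 2.4 over 12. These figures rest on an assumed AE rate, constant hazards, no restarts, and the SAP's 15-20% as the proportion stopping by month 12.

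The tables are descriptive and claim no causality. The consequence is an incidence figure that cannot be read as incidence during Valchlor use, not a demonstrated bias.

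**What to change.** 1. Reconcile the Assessment Schedule sentence with the Table 1 footnote and with protocol 5.6.1, 7.1.2 and 7.2. State in the SAP which events beginning more than 30 days after discontinuation the eCRF actually holds.
2. Keep the protocol's on-study summary, from enrollment to end of study. Add a version of Tables 18 and 19, and of the dermatitis incidence, limited to onset from enrollment to 30 days after Valchlor discontinuation. Show later events, and events ongoing at enrollment, separately.
3. Say how restarts of Valchlor are treated when the window is derived from the treatment log.
4. Add Valchlor status at onset to Listing 1, so that SAEs can be listed with and without non-concurrent events as 5.7.5 requires. Relationship need not be added, since Listing 9 has it.

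The cost is SAP wording, one extra tabulation and one derived column, using dates already collected. The restricted table will show somewhat lower AE percentages. No events are lost, because the full on-study summary stays.
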